6.2.1.3. Medical/Surgical History and Baseline Physical Examination

Medical history will be classified by SOC and PT using the latest available version of standardized MedDRA and will be reported by treatment group and overall for the Safety Set.

Abnormal physical examination results at baseline and postbaseline will be summarized by treatment group for the Safety Set.

By-participant listings of medical/surgical history and abnormal physical examination results will also be produced.

6.2.2. Prior and Concomitant Medications / Therapies

Prior and concomitant medications and procedures will be summarized using the Safety Set.

Prior medications or procedures are defined as medications or procedures taken within 30 days before the start of Screening or during the Screening Period before the first dose of study intervention, as well as any meningococcal vaccine administered within the last 3 years prior to the first dose of study intervention.

Concomitant medications or procedures are defined as medications or procedures received by the participants on or after the first study intervention date (Day 1), including those started before Day 1 and continued after Day 1.

Medications will be coded using the World Health Organization Drug Dictionary (WHO-DRUG) version in use by Alexion at the time of the analysis while nonpharmacologic therapies and procedures (any therapeutic intervention, such as surgery/biopsy or physical therapy) will be coded using MedDRA.

Prior medication and concomitant medication summaries will be presented by WHO-DRUG Anatomical Therapeutic Chemical (ATC) Level 3 and by WHO-DRUG generic name using number [%] of participants by treatment group. Procedures will be summarized similarly but presented by MedDRA Class and PT. In addition, protocol-required vaccinations will be summarized similarly.

By-participant listings of prior and concomitant medications, procedures, and protocol-required vaccinations will also be produced.

6.2.3. Allowed Concomitant Therapy and Additional Standard-of-Care Therapy

Allowed concomitant therapy and additional standard-of-care therapy medications will be summarized using the Safety Set.

Allowed concomitant therapy for participants in the LN cohort consists of standard-of-care treatment for induction and maintenance of LN including corticosteroids and MMF or MMF equivalent. Allowed concomitant therapy for participants in the IgAN consists of standard-of-care treatment including maximally tolerated dose of RAS-blocking agents such as angiotensin-converting enzyme (ACE) inhibitors or angiotensin II receptor blockers (ARBs).

Allowed concomitant therapy use within 3 months prior to Screening and up to the first dose of study intervention will be presented by WHO-DRUG ATC Level 3 and by WHO-DRUG generic name using number [%] of participants by treatment group. In addition, allowed concomitant therapy use at Baseline, including the daily dose at baseline (LN cohort only), will be summarized by treatment group. Changes in allowed concomitant therapy during the study as well as the reason for change will be summarized by treatment group. For the LN cohort, allowed concomitant therapy use at Baseline will include all therapies during the Screening Period and the first study day.

For the LN cohort, participants will receive additional standard-of-care therapy in the event of a protocol-defined renal flare, severe extrarenal SLE flare, or suboptimal response. Additional standard-of-care therapy is defined as intensification of current standard of care or introduction of new immunosuppressive therapies. Additional standard-of-care therapy will be presented by WHO-DRUG ATC Level 3 and by WHO-DRUG generic name by type of flare using number [%] of participants by treatment group.

By-participant listings of allowed concomitant therapy and additional standard-of-care therapy will also be produced.

6.2.4. Protocol Deviations

Protocol deviations will be determined per the standard operating procedure “Identification, Handling, and Documentation of Protocol Deviations” (SOP-G-CL-0044). The number and percent of patients with specific protocol deviations will be summarized for all enrolled participants by important and nonimportant deviations. Protocol deviations will be presented overall as well as separately for those related to COVID-19.

To ensure completeness of the list of protocol deviations, the following will be verified programmatically from the database:

1. Participants from whom informed consent was not obtained
2. Participants who violated any inclusion/exclusion criteria.
3. Participants who received any disallowed medication or therapy
4. Participants randomized to the ravulizumab treatment group who did not receive all of the planned number of doses during the 26-week randomized treatment period.

Protocol deviations from monitoring reports and other relevant sources will also be reviewed, and any important deviations will be included in the list that is summarized and reported.

Summary statistics will be presented by treatment group and overall.

6.3. Appendix 3: Instrument Scoring Details

6.3.1. SF-36v2

The SF-36v2 is a self-administered questionnaire designed to assess generic health-related QoL in healthy and ill adult populations. Eight health domain scores (PF, SF, RP, BP, GH, MH, RE, and VT) and 2 component scores (PCS and MCS) will be calculated.

The SF-36v2 Health Survey with the standard (4-week) recall period will be used in this study. The OPTUM PRO CoRE 1.5 Smart Measurement System will be used to derive the 8 domain scores and 2 component scores. The algorithms used by the software are described below (as excerpted from the User's Guide).

6.3.1.1. Data Cleaning and Item Recoding

First, the data are checked for out-of-range values. Out-of-range values are any values that are outside the range of acceptable item response values for the SF-36v2 Health Survey. Out-of-range values will be converted to missing values. Next, 10 items (BP01, BP02, GH01, GH03, GH05, VT01, VT02, SF01, MH03, MH05) are reverse scored. Reverse scoring of these items is required so that a higher item response value indicates better health for all SF-36v2 Health Survey items and summary measures.

6.3.1.2. Item Recalibration

For most of the SF-36v2 Health Survey items, research to date offers good support for the assumption of a linear relationship between the item scores and the underlying health concept defined by their scales. However, empirical work has shown that 2 items, items GH01 and BP01, require recalibration to satisfy this important scaling assumption. The Bodily Pain (BP) scale requires additional scoring rules because the items offer both different numbers and different content of response choices and administration of item BP02 depended upon the response to an item like item BP01 in past studies.

6.3.1.3. Computation of Raw Scores

After recoding and recalibrating the required item values, a raw score is computed for each scale. This score is the simple algebraic sum of the final values for all items in that scale.

6.3.1.4. Transformation of Raw Scale Score to 0 to 100 Scores

The next step involves transforming each raw scale score to a 0 to 100 scale. This transformation converts the lowest and highest possible scores to zero and 100, respectively. Scores between these values represent the percentage of the total possible score achieved.

6.3.1.5. Transformation of 0 to 100 Scores to T-score Based Scores

The first step in T-score based scoring consists of standardizing each SF-36v2 Health Survey scale using a z-score transformation. A z-score indicates how far a score deviates from the mean in SD units. The z-score for each scale is computed by subtracting the mean 0 to 100 score observed in the 2009 general US population from each SF-36v2 Health Survey scale score (0 to 100) scale and dividing the difference by the corresponding scale SD observed in the 2009 general US population. The means and SD s utilized are dependent upon the recall period option chosen by the user, based on the SF-36v2 Health Survey form used to collect the data being scored.

The next step of the T-score based scoring is to linearly transform each SF-36v2 Health Survey z-score to have a mean score of 50 and a SD of 10. This is done by multiplying each SF-36v2 Health Survey z-score by 10 and adding the resulting product to 50. These are referred to as ‘norm-based’ scores. The norm-based scores will be used for the 8 domain scores.

6.3.1.6. Scoring the SF-36v2 Health Survey Component Summary Measures

The first step in scoring the component summary measures consists of standardizing each SF-36v2 Health Survey scale using a z-score transformation as described previously. The z-score for each scale is computed by subtracting the mean 0 to 100 score observed in the 2009 general US population from each SF-36v2 Health Survey scale score (0 to 100) scale and dividing the difference by the corresponding scale SD observed in the 2009 general US population. The means and SD utilized are dependent upon the recall period option chosen by the user, based on the SF-36v2 Health Survey form used to collect the data being scored.

After a z-score has been computed for each SF-36v2 Health Survey scale, the second step involves computation of aggregate scores for the physical and mental summaries using weights (factor score coefficients) derived from the 1990 general US population. These are the same weights as those used to score PCS and MCS from the SF-36 Health Survey. An aggregate physical score is computed by multiplying the z-score of each SF-36v2 Health Survey scale by its associated physical factor score coefficient and summing the 8 products. If any of the scale scores are missing, then the aggregate physical score is not computed. An aggregate mental score is computed by multiplying the z-score of each SF-36v2 Health Survey scale by its associated mental factor score coefficient and summing the 8 products. If any of the scale scores are missing, then the aggregate mental score is not computed.

The third step involves transforming the aggregate physical and mental summary scores to the T-score Based (50, 10) scoring. This is done by multiplying each aggregate summary score obtained from Step 2 by 10 and adding the resulting product to 50.

6.3.1.7. Handling of Missing Items

The maximum data recovery option will be used for missing data estimation. This results in the application of algorithms that compute a scale score for those respondents whom have answered at least 1 item that represents that construct. For the PF scale, item parameters obtained through item response theory methods are used to estimate a missing value on an item based upon a respondent's responses to answered items. For the 7 remaining scales, a person-specific estimate based on the mean response to the answered items on the scale is used to estimate a missing value. Additionally, a PCS and MCS score is calculated for those respondents whom have calculated scores on at least 7 of the 8 SF-36v2 Health Survey scales. However, PCS is not estimated if the PF scale is missing, and MCS is not estimated if the MH scale is missing.

6.3.2. EQ-5D-5L

The EQ-5D-5L version will be used in this study. EQ-5D health states, defined by the EQ-5D descriptive system, may be converted into a single summary index by applying a formula that attaches values (also called weights) to each of the levels in each dimension. The index can be calculated by deducting the appropriate weights from 1, the value for full health (ie, state 11111). The collection of index values (weights) for all possible EQ-5D health states is called a value set. EQ-5D-5L index scores for this study will be obtained using the composite time trade-off (cTTO) method based on the Tobit model ([Pickard, 2019](#)). The calculation is illustrated below.

US cTTO	Example: the value for health state 21354	
Full health (11111)		Full Health = 1
Mobility level 2	-0.096	-0.096
Mobility level 3	-0.122	
Mobility level 4	-0.237	
Mobility level 5	-0.322	
Self-Care level 2	-0.089	0
Self-Care level 3	-0.107	
Self-Care level 4	-0.220	
Self-Care level 5	-0.261	
Usual Activity level 2	-0.068	
Usual Activity level 3	-0.101	-0.101
Usual Activity level 4	-0.255	
Usual Activity level 5	-0.255	
Pain/Discomfort level 2	-0.060	
Pain/Discomfort level 3	-0.098	
Pain/Discomfort level 4	-0.318	
Pain/Discomfort level 5	-0.414	-0.414
Anxiety/Depression level 2	-0.057	
Anxiety/Depression level 3	-0.123	
Anxiety/Depression level 4	-0.299	-0.299
Anxiety/Depression level 5	-0.321	

US cTTO	Example: the value for health state 21354
Health State Index Score	= 1 - 0.096 - 0 - 0.101 - 0.414 - 0.299 = 0.090

If data for some but not all dimensions are missing at a specific time point, data for the missing dimension(s) from the last available assessment prior to the time point with missing data will be used in the US cTTO calculation. If all dimensions are missing, the last available US cTTO score prior to the time point with missing data will be used.

The EQ VAS records the respondent's self-rated health on a vertical VAS where the endpoints are labeled 'The best health you can imagine' for 100 and 'The worst health you can imagine' for 0. Missing values will be coded as '999.' If there is a discrepancy between where the respondent has placed the X and the number written in the box, number in the box will be used for VAS.

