5.4.1. Proteinuria

The percentage change from baseline in proteinuria at Week 50 will be analyzed using a mixed-effect model for repeated measures (MMRM) using all available longitudinal data (either complete or partial). The model will include change from baseline in log-transformed proteinuria as the response variable and fixed, categorical effects of treatment group, randomization stratification factor, visit, and treatment group by visit interaction as well as a fixed, continuous effect of baseline log proteinuria as a covariate. An unstructured covariance matrix will be used to model the correlations among repeated measurements within each participant. If this analysis fails to converge, a first-order autoregressive covariance matrix will be used. The Kenward-Roger approximation will be used to estimate denominator degrees of freedom.

For the IgAN cohort, participants initially randomized to the placebo treatment group will switch to receive ravulizumab at Week 26. Therefore, percentage change from baseline in proteinuria at Week 50 will be summarized descriptively for each treatment group and for each visit from the MMRM analysis, and no formal treatment comparison will be made.

For the LN cohort, the treatment effect will be evaluated using a contrast for treatment group-by-visit term at Week 50. The point estimate and 2-sided 90% CI for the mean difference of log-transformed proteinuria will be back-transformed (via exponentiation) to obtain the GMR and corresponding 2-sided 90% CI. The values will then be expressed as percentage change in adjusted geometric mean of proteinuria at Week 50 relative to baseline.

This analysis will be performed 2 ways:

- Data collected on or after receipt of additional standard-of-care therapy (for the LN cohort only) will be imputed using the value collected at the time of renal flare, extrarenal SLE flare, suboptimal response, and data collected on or after treatment discontinuation will be assumed missing and handled in the MMRM as MAR.
- Data collected on or after receipt of additional standard-of-care therapy or treatment discontinuation will be assumed missing and handled in the MMRM as MAR.

In addition to the proteinuria analyses based on 24-hour urine collections, the percentage change from baseline in spot UPCR at each scheduled visit will be analyzed using an MMRM in a similar manner as above.

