5.5. Tertiary/Exploratory Endpoint Analysis

The exploratory analyses will be based on the FAS. These analyses will be descriptive in nature, and no adjustment for multiplicity will be performed. In addition, there will be no imputation for missing data or data collected on or after the receipt of additional standard-of-care therapy (for LN cohort) or treatment discontinuation unless otherwise specified below.

Summary statistics will be computed and displayed by treatment group and by visit, where applicable. Descriptive statistics for continuous variables will minimally include the number of participants, mean, SD, minimum, median, and maximum. For categorical variables, frequencies and percentages will be presented.

The analyses for participants in the LN cohort and participants in the IgAN cohort will be conducted and reported separately. Participants in each disease-specific cohort will be analyzed as randomized, regardless of actual treatment received.

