5.5.3. EQ-5D-5L

The EQ-5D-5L is a self-assessed, health-related QoL questionnaire. It is a measure of health status consisting of 2 parts. The first part assesses health in 5 dimensions including mobility, self-care, usual activities, pain/discomfort, and anxiety/depression. Each level is rated on a scale that describes the degree of problems in that area (ie, I have no problems walking about, slight problems walking, moderate problems walking, severe problems walking, or unable to walk). This part of the EQ-5D-5L questionnaire provides a descriptive profile that can be used to generate a health state profile. For example, a participant in health state 12345 would have no problems with mobility, slight problems with self-care (washing or dressing), moderate problems with doing usual activities, severe pain or discomfort and extreme anxiety or depression. The EQ-5D-5L health states can be represented by a single summary number (index value), which reflects how good or bad a health state is according to the preferences of the general population of a country/region. A health state index score will be calculated using a US-specific value set ([Pickard, 2019](#)). The second part consists of a visual analog scale (VAS) on which the participant rates their perceived health from 0 (the worst imaginable health) to 100 (the best imaginable health).

For both cohorts, the EQ-5D-5L index score and VAS score will be summarized by treatment group at baseline and each postbaseline time point using descriptive statistics for continuous variables for the observed value as well as the change from baseline.

The longitudinal changes in EQ-5D-5L scores will also be analyzed using the same MMRM method specified in Section [5.4.1](#). Data collected on or after receipt of additional standard-of-care therapy or treatment discontinuation will be assumed missing and handled in the MMRM as MAR.

Refer to Section [6.3.2](#) for a more detailed description of the EQ-5D-5L calculation and scoring methods.

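### A wholly missing EQ-5D-5L index score is replaced by the last available score, so copied values can enter the planned MMRM as if they had been observed

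*SAP*

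**What the plan says.** SAP 6.3.2 has two filling rules for the EQ-5D-5L index.

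- Some dimensions missing at a visit: "data for the missing dimension(s) from the last available assessment prior to the time point with missing data will be used in the US cTTO" (the index formula).
- No dimension answered: "If all dimensions are missing, the last available US cTTO score prior to the time point with missing data will be used".

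Neither rule limits the age of the copied value, restricts it to visits on treatment, or asks for a flag. The VAS, the other EQ-5D-5L score, has no carry-forward; a missing VAS is coded 999.

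SAP 5.1.4 sends missing quality-of-life data to the instrument instructions in Section 6.3, so these rules are operative.

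For the analysis, SAP 5.5.3 states: "The longitudinal changes in EQ-5D-5L scores will also be analyzed using the same MMRM method specified in Section" 5.4.1. SAP 5.4.1 describes that model as using whatever longitudinal data are available, including from participants with incomplete series. SAP 5.5.3 adds: "Data collected on or after receipt of additional standard-of-care therapy or treatment discontinuation will be assumed missing and handled in the MMRM as MAR". The opening of SAP 5.5 says that "there will be no imputation for missing data or data collected on or after the receipt of additional standard-of-care therapy" or treatment discontinuation, but the same sentence exempts anything specified otherwise later.

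**The concern.** A mixed model leaves a missed visit missing and uses the participant's other visits, through the estimated correlation, under the MAR assumption. If the score is filled beforehand, the model never sees a gap. MAR is then silently replaced by the assumption that health has stood still since the last questionnaire, and the copy counts as a full observation.

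Two things are at stake. The estimated change in the index can be pulled toward an earlier state, by different amounts in the two arms. The result can also look more precise than the observed data allow. In addition, because the order of scoring and setting to missing is open, two programmers could both follow the SAP and build different datasets.

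**Working it through.** **1. The plan's own figure.** The worked index in SAP 6.3.2 for health state 21354 reproduces: 1 − 0.096 − 0 − 0.101 − 0.414 − 0.299 = 0.090. The scoring formula is not in question.

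**2. Age of a copied score.** In the schedules of activities (Protocol 1.3, Tables 1 to 4), both cohorts complete the questionnaire on Day 1, Day 71 (Week 10), Day 183 (Week 26) and Day 351 (Week 50).

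- Week 26 filled from Week 10: (183 − 71)/7 = 16 weeks old.
- Week 50 filled from Week 26: (351 − 183)/7 = 24 weeks old.
- If the preceding visit is missing too: (183 − 1)/7 = 26 weeks, and (351 − 71)/7 = 40 weeks.

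These are scheduled days. Visit windows move them slightly, and a participant who leaves may supply a later score at the early discontinuation visit.

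**3. Changes forced to zero.** A score copied from Day 1 equals baseline, so its change is exactly 0. In the IgAN placebo group, SAP 5.1.2 and 5.4 redefine the Extension Period baseline as the last value before ravulizumab, which is Week 26. A missing Week 50 filled from Week 26 therefore gives a change of 0 across the switch to active drug.

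**4. Order of operations.** The SAP does not fix it.

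- *Score first, then set post-event data to missing.* Copies after additional standard-of-care therapy or treatment discontinuation are removed. Copies for visits missed on treatment stay in.
- *Set post-event data to missing first, then score.* Section 6.3.2 refills those same visits, against SAP 5.5.3. Copies for visits missed on treatment stay in as well.

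Either way some copied scores reach the model as observed.

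**5. Illustration of the effect.** The documents give no inputs for this, so all are assumed: 40 against 20 participants, SD of change 0.15, correlation 0.6 between Week 26 and Week 50 change, and 10% to 30% missing at Week 50, unrelated to outcome. With missing fraction m, carry-forward gives an arm mean of

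Week 50 mean − m × (Week 50 mean − Week 26 mean).

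The simulation (3,000 runs per row) compares a simple difference in means after carry-forward with a MAR likelihood estimate that uses Week 26. It is not the full planned MMRM.

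| Missing, ravulizumab/placebo | True difference | Carry-forward, by formula | Carry-forward, simulated | MAR, simulated |
|---|---|---|---|---|
| 10%/10% | 0.06 | 0.095 − 0.038 = 0.057 | 0.0559 | 0.0589 |
| 20%/20% | 0.06 | 0.090 − 0.036 = 0.054 | 0.0542 | 0.0600 |
| 30%/10% | 0.06 | 0.085 − 0.038 = 0.047 | 0.0472 | 0.0602 |
| 10%/30% | 0.06 | 0.095 − 0.034 = 0.061 | 0.0605 | 0.0597 |
| 10%/30% | 0 | 0.095 − 0.085 = 0.010 | 0.0103 | 0.0001 |
| 30%/10% | 0 | 0.085 − 0.095 = −0.010 | −0.0102 | −0.0002 |

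In the first four rows, mean change goes from 0.05 at Week 26 to 0.10 at Week 50 on ravulizumab and from 0.02 to 0.04 on placebo. In the last two, both arms go from 0.05 to 0.10. With no change between visits there is no bias.

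In the 20%/20% row the standard error is 0.0411 with carry-forward and 0.0443 under MAR; 0.0411/0.0443 = 0.928, about 7% smaller. The smaller figure describes a mixture of Week 26 and Week 50 states. Read as precision about the Week 50 change, it is too small.

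**The case against.** The strongest defence is that the SAP permits the rule. The no-imputation statement in SAP 5.5 carries its own exemption, and SAP 5.1.4 delegates missing quality-of-life data to Section 6.3. A reader might infer that 6.3.2 contradicts 5.5; with that exemption and delegation, the documents do not support this.

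Nor are 6.3.2 and 5.5.3 irreconcilable. The MAR sentence in 5.5.3 covers only data on or after the two named events, not a visit missed on treatment. If scores are derived first and post-event scores then set to missing, both rules are obeyed. What is missing is the order.

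It is also tempting to put a number on the harm: 10% dropout among 60 gives 6 copied scores, and √(54/60) = 0.949 suggests an interval about 5% too narrow. That does not hold up. The 10% belongs to the primary endpoint's sample size, and participants who have stopped treatment are those whose post-event scores 5.5.3 treats as missing. The formula also ignores what the MMRM recovers from other visits: at 20% missing it gives √(48/60) = 0.894, an 11% narrowing, against about 7% in the simulation.

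Finally, one might say the index becomes non-comparable with SF-36v2 and FACIT-Fatigue. Those instruments do fill only within a visit (SAP 6.3.1.7 and 6.3.3), but no comparison across instruments is planned.

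All of this limits the point. None of it explains why a model that needs no filled values should receive copied ones.

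**Conclusion.** The point stands, at minor severity. Index scores for visits missed on treatment will enter the MMRM and the descriptive summaries as if observed. Depending on an unstated order, post-event visits may be refilled as well, although SAP 5.5.3 says such data "will be assumed missing and handled in the MMRM as MAR".

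The direction of any bias is not predictable. Under the assumptions above, carry-forward shrank a real difference, left it nearly unchanged, or created one of about 0.01 where none existed, depending on which arm had more missed visits. The actual size cannot be derived from the documents.

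The reach is narrow. Only the EQ-5D-5L index is carried forward, not the VAS. The endpoint is exploratory and descriptive, with no multiplicity control, and the primary and secondary results are untouched.

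**What to change.** In SAP 6.3.2, delete the sentence that carries the whole index score forward. Because SAP 5.1.4 points to Section 6.3 for a rule, replace it with one: a wholly missing index score stays missing and is handled as MAR by the MMRM in SAP 5.5.3. Add that no index value is filled on or after additional standard-of-care therapy or treatment discontinuation, which settles the order of operations. If carry-forward is still wanted, keep it only as a labelled sensitivity analysis.

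The rule for single missing dimensions is a separate choice. Dropping the index whenever any one dimension is missing would discard answers that were given, and this point does not require it.

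The cost is a short text edit, with no new data and no design change. The descriptive tables will hold fewer scores and the interval will be slightly wider.
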